5.2 Data Source

Truven MarketScan Claims Database (01JUL2013-30JUN2018)

The MarketScan[®] claims databases offer the largest convenience sample available in proprietary databases, with 69 million unique patients since 1996. In the most recent data year, MarketScan[®] claims databases contain data on 29 million covered lives. The stability of MarketScan[®] data sources allows superior continuity of patients over multiple years, which is generally longer than other claims databases. This is due to the fact that the majority of MarketScan[®] data is sourced from large employers. Employer-provided data also allow tracking of patients across health plans. This tracking ability is useful because people change health plans more often than they change jobs, and these data are able to capture patients who are “lost” in plan-based data sources - upward of 17% of patients in those databases. In the most recent 5 years of MarketScan[®] data, nearly 29 million patients (73%) have at least 12 months of continuous enrollment.

The MarketScan[®] claims databases contain complete information on outpatient prescriptions. These databases afford distinct advantages over others that track only prescription fills. MarketScan[®] data allow for disease type identification (from medical claims) and can be used to determine whether clinical, demographic, and provider characteristics influence prescribing patterns. Because individual patients’ prescription fills are recorded, therapies prescribed

[2018-7241 Study Identifier] Observational Study Protocol

concurrently (and presumably used in combination) can also be identified. This provides vital information about actual drug use patterns, as opposed to individual drug prescription trends.

LCED (01APR2013-31MAR2018))

The Truven MarketScan administrative claims can be linked to the IBM Explorys EMR data, which allows access to complete longitudinal patient records from all patient's health care providers. Therefore, the integrated dataset provides comprehensive patient data to allow for a complete understanding of the research questions related to health care. For example, the powerful dataset provides licensed access to the following key information, including:

- Complete payment/charge information
- Outpatient prescription for drugs
- Claims and eligibility data from multiple U.S. payers
- Vitals and biometrics
- Patient reported outcomes (PHQ 9, pain scores etc)
- Laboratory results

VHA Database (01APR2013-31MAR2018)

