5.3. Study Population

5.3.1 Selection Criteria

Patient selection criteria for the U-500R Syringe Initiators [Index Event 1a]:

- Include patients who had ≥ 1 prescription claim for U-500R vial during the identification period (VHA and LCED: 01JAN2014-30JUN2017; Truven: 01APR2014-30SEP2017)—the first prescription claim for U-500R vial will be designated as index Event 1a (U-500R syringe initiation), and the date will be designated as the index date;
- Include patients who had ≥ 2 claims with an ICD-9/10-CM code (Appendix 1) for T2DM in any position (primary/secondary) at any time prior to the index date;
- Exclude patients who had both T1DM and T2DM, had no oral anti-diabetic drug (OADs; Appendix 1) other than metformin, and the ratio between the number of T1DM and T2DM claims > 0.5 at any time in the study period (VHA and LCED: 01APR2013-31MAR2018; Truven: 01JUL2013-30JUN2018);
- Include patients who were aged ≥ 18 years on the index date;
- Include patients who had continuous health plan enrollment with medical and pharmacy benefits for ≥ 9 months pre- and post-index event;
- Exclude patients with no evidence of insulin including U-500R (any type; Table 2) in the 9 months pre-index period (baseline);

[2018-7241 Study Identifier] Observational Study Protocol

- Exclude patients with ≥ 1 prescription claim for U-500R use in the 9 months pre-index period;
- Include patients who had ≥ 1 prescription claim for any insulin other than U-500R in the 9-month pre-index period;
- Include patients who had ≥ 1 HbA1c measurement within 90-day pre-index or 30-day post-index event;
- Include patients who had ≥ 1 HbA1c measurement after the 30-day post-index period at any time in the 9-months follow-up period;
 - Patients with ≥ 1 HbA1c measurement after the 30-day post-index and within 30 days prior to the end of the 9-months follow-up period will be flagged; and
 - Patients with ≥ 1 HbA1c measurement after the 30-day post-index and within 2 months prior to the end of the 9-months follow-up period will be flagged;
- Exclude patients who had ≥ 1 claim with a ICD-9/10-CM code (Appendix 1) for secondary diabetes, gestational diabetes, diabetes complicating pregnancy, childbirth, or puerperium, or non-clinical diabetes at any time during the 9-month baseline period;
- Exclude patients who had claims indicating pump use (Appendix 2) in the 9-month post-index (follow-up) period;

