5.4 Time Periods

The study period will range from 01APR2013-31MAR2018 for VHA and LCED; and 01JUL2013-30JUN2018 for Truven MarketScan claims. The identification period will be 01JAN2014-30JUN2017 for VHA and LCED; and 01APR2014-30SEP2017 for Truven MarketScan claims; the baseline and follow-up periods will be 9 months pre- and 9 months post-index date, respectively (Figures 1-3).

[2018-7241 Study Identifier] Observational Study Protocol**5.5 Variables/Measures**

Table 3 presents the study variables and operational definitions.

Table 3 Variables and Definitions

Variable	Source	Definition
Exposure		
Insulin use	Truven: Outpatient pharmacy claims table VHA: Pharmacy file	Index Event 1a : any insulin use other than U-500R in the pre-index and U-500R syringe use in the post-index period; Index Event 1b : any insulin use other than U-500R in the pre-index and U-500R Kwikpen use in the post-index period; and Index Event 2 : U-500R syringe use in the pre-index and U-500R Kwikpen use in the post-index period.
Baseline Characteristics*		
Age	Truven: Inpatient service table, outpatient service table, outpatient pharmacy claims table VHA: Enrollment file	Age will be retained in the dataset as a continuous variable for groups aged 18-25, 26-35, 36-45, 46-55, 56-64, and ≥ 65 years.
Sex	Truven: Inpatient service table, outpatient service table, outpatient pharmacy claims table VHA: Enrollment file	A flag will be created for male and female patients.
Race (only VHA)	VHA: Enrollment file	A flag will be created for White, Black, and other race patients.
U.S Region (only Truven)	Truven: Inpatient service table, outpatient service table, outpatient pharmacy claims table	A flag will be created for patients belonging to Northeast, Northcentral, South and West regions
Medicare eligibility (Only Truven)	From Truven	A flag will be created for patients who are enrolled in Truven Medicare
Body mass index (BMI)	VHA: Vital Status file	BMI on the index date will be calculated and reported as a continuous variable.
Quan-Charlson comorbidity index (CCI) Score ¹⁶	Truven: Inpatient service table, outpatient service table VHA: Inpatient and outpatient files	Quan-CCI score will be constructed using enhanced ICD-9/10-CM codes for 17 different comorbid conditions.

[2018-7241 Study Identifier] Observational Study Protocol

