a longitudinal feature in which a continuous outcome variable is measured for the same subject repeatedly over the time period. Based on the distribution of the data, observations measured for the same subject are likely to be correlated over the study period and these data are considered as “multilevel” data. In addition, mixed linear model has a mixed effect consisting both fixed and random effects. For this objective, mixed linear model helps to evaluate the effect of both time varying and time-independent variables on the costs, while taking into account for correlation due to multiple assessments from the same individual. In the current model, costs which are measured at two time intervals (before and after the index event; U-500R initiation), will be considered the dependent variable. Observed TDD will be considered as the time varying covariates in the model (measured both before and after the index date), and the time-independent covariates will include the demographic and clinical characteristics.

The complete list of covariates will include:

- age
- sex
- region
- baseline CCI score
- observed TDD from claims
- Medicare (yes/no)
- time (pre/post)

Note: For all the multivariate analyses the covariates will be included as per the availability in each of the VHA, Truven claims, linked Truven claims and EMR data and pooled VHA and linked Truven data. Age, sex, region, medicare (yes/no), and CCI score will be assessed during pre-index period. Observed TDD will be calculated during the entire pre-index and post-index periods, respectively.

Adherence will not be included as one of the covariates here due to the high collinearity between time and adherence. Hence, further mediation analysis will be performed to determine the mediator effect of adherence on costs.

Mediation Analysis:

Mediation analysis following the Baron and Kenny’s steps will be considered to understand the impact of index event (time) on costs through potential mediators. Adherence is considered as a potential mediator between the costs and time. The key steps in mediation analysis include a model of the mediator (adherence) as a function of the predictor (time) and a model of the outcome (costs) as a function of both the mediator (adherence) and the predictor (time). Bootstrapping method will be used to test the effect of mediator. The detailed steps are described below:

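### The Objective 3 cost model fixes Medicare status at its pre-index value, so it cannot adjust the before/after cost contrast for a change of payer; the likely effect is small and the remedy is cheap.

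*Protocol*

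**What the plan says.** Protocol section 6.4.1, Research Objective 3, specifies a generalized linear mixed model with log link for total and out-of-pocket costs, with two records per patient (before and after initiation). The model is described as able to take both time-varying and time-independent variables. Its covariates are introduced with "The complete list of covariates will include" and are age, sex, region, baseline CCI score, observed TDD, Medicare (yes/no) and time. Only observed TDD is named as varying over time. The note beneath says: "Age, sex, region, medicare (yes/no), and CCI score will be assessed during pre-index period". Table 3 defines the Medicare variable as a single flag, "A flag will be created for patients who are enrolled in Truven Medicare", with no rule for a patient whose status changes.

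Three other provisions bear on this:
- The windows (section 5.4): "the baseline and follow-up periods will be 9 months pre- and 9 months post-index date, respectively".
- The enrollment criterion (section 5.3.1): "Include patients who had continuous health plan enrollment with medical and pharmacy benefits for" at least 9 months on each side of the index event. It does not mention remaining with the same payer or plan.
- The description of MarketScan (section 5.2): "Employer-provided data also allow tracking of patients across health plans".

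The mediation text of Objective 3 treats time as the impact of the index event on costs and calls its effect the primary interest. The unadjusted comparison is a paired t-test.

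**The concern.** Objective 3 has no comparator group. Each patient is compared with himself or herself, so the coefficient for time is the result. Anything other than U-500R that changes between the two windows, and that no time-varying covariate captures, goes into that coefficient.

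A change of payer is one such thing. A patient who moves from commercial cover to Medicare, for example on reaching 65, may face different cost sharing from that day. (Age 65 as the usual entry point is a general assumption, not taken from the protocol.) The listed Medicare covariate looks as if it deals with this, but fixed at its pre-index value it does not. The affected quantities are the time effect on out-of-pocket and total costs, and the direct effect, total effect and percentage mediated that follow from it.

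**Working it through.** The protocol gives no cost figure, payer-switch rate or sample size for Objective 3 (Table 4 covers VHA only), so there is no stated figure to reproduce.

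**1. Why a constant flag cannot help.** Write the model as log E(Y_it) = a + b·t + c·M_i + other terms, with t = 0 before and 1 after. For one patient the after-minus-before contrast in the Medicare and time terms is b + c(M_i − M_i) = b. With a period-specific flag it is b + c(M_i1 − M_i0), so a payer change is carried by c rather than by b.

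**2. Size with no drug effect.** Assumed inputs: share on Medicare at baseline p = 0.25; share of all patients moving to Medicare s = 0.05; Medicare multiplies out-of-pocket cost by f = 0.6 or 1.6.

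- No Medicare term: ratio = 1 + s(f − 1)/[(1 − p) + p·f]
  - f = 0.6: 1 − 0.05 × 0.4/0.90 = 0.978
  - f = 1.6: 1 + 0.05 × 0.6/1.15 = 1.026
- Frozen flag: the ratio is 1 among those already on Medicare and 1 + (s/(1 − p))(f − 1) among the rest. Weighting by patients:
  - f = 0.6: 0.25 × 1 + 0.75 × 0.973 = 0.980
  - f = 1.6: 0.25 × 1 + 0.75 × 1.040 = 1.030
- Flag per period: the ratio is 1.

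A simulation with the same inputs agrees (200,000 patients, gamma model with log link; as a simplification, no random effect was fitted):

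| f | no Medicare term | frozen flag | flag per period |
|---|---|---|---|
| 0.6 | 0.976 | 0.978 | 0.998 |
| 1.6 | 1.028 | 1.032 | 1.002 |

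The frozen flag removes essentially none of the shift. The per-period flag removes nearly all of it.

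**3. Range of switch rates (all assumed).**
- If 2-6% of patients are aged 64 at index, 9/12 of them, or 1.5-4.5%, turn 65 during follow-up. The no-term formula in step 2 then gives 0.993 to 0.980 for f = 0.6 and 1.008 to 1.024 for f = 1.6.
- Alternatively, if 40-60% are aged 55-64, that is 4-6% per year of age and 3-4.5% per 9-month window. With a 20-40% change in cost sharing the mean moves by 3% × 20% = 0.6% to 4.5% × 40% = 1.8%.
- Patients change partway through a window. Those turning 65 after index contribute on average half the change, but those turning 65 before index contribute the other half, so the total remains about s.

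**4. Plan-year position.** The Truven identification period is "01APR2014-30SEP2017 for Truven MarketScan claims", which contains 1,279 possible index dates.
- With dates evenly spread, January-March days average 70.9 before and 67.9 after, in windows averaging 273.9 and 274.0 days.
- If January-March spending is k times that of other months (assumed), the null ratio is [274.0 + (k − 1) × 67.9]/[273.9 + (k − 1) × 70.9]. This is 0.997 for k = 1.3 and 0.991 for k = 2.0.
- A 1 January falls in 78.4% of pre-index and 78.7% of post-index windows.
- A constant-spending model with a January deductible reset, under four assumed benefit designs, gives a cohort ratio of 0.96-1.00.

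If Kwikpen index dates began only at a later date (assumed starts), the picture depends on that date:

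| First index date | windows with 1 January, pre / post | modelled null ratio |
|---|---|---|
| 01JAN2016 | 85.4% / 71.7% | 0.92-0.96 |
| 01OCT2016 | 74.8% / 75.3% | about 1.00 |
| 01JAN2017 | 99.6% / 67.0% | 0.82-0.91 |

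**The case against.** The protocol is consistent in treating Medicare as a baseline characteristic, and an analysis plan that is not shown might add sensitivity analyses. That does not dispose of the point: the covariate list is called complete and the timing of the Medicare flag is fixed in the protocol text, so this is not a detail left open.

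Continuous enrollment with medical and pharmacy benefits for 9 months on both sides limits how many payer changers remain. The remark about following patients across plans is general database description and says nothing about how often payers change in this cohort. Both objections stand. They make the effect small but do not exclude it.

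A reader might also infer that deductible resets are, in general, credited to U-500R. The documents do not support that. With evenly spread index dates the resets fall almost equally before and after. Ratios for a single index quarter can be large (1.36-1.83 for October-December in the deductible model), but they are not the bias of the planned cohort estimate. A material shift needs clustered index dates or a short accrual period. Section 5.1 says only that Kwikpen is recently available and gives no launch date, and that argument does not apply to syringe initiators.

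**Conclusion.** The point holds for Medicare. A status fixed before the index date cannot adjust a within-patient cost contrast, so payer changes can enter the time effect and the mediation. The size is roughly 1-3% of mean out-of-pocket cost, in either direction. It rests on assumed values for the share on Medicare, the share changing payer and the change in cost sharing, none of which the documents give. This is a minor but easily avoided weakness.

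On plan-year position only a check is warranted. With even accrual the shift is under 1% in the day-count calculation and at most about 4% in the deductible model. Whether it is larger for Kwikpen depends on an index-date distribution that the protocol does not report.

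**What to change.** 1. In the Objective 3 note and the Table 3 Medicare row, define Medicare status separately for the pre- and post-index periods, for example as the share of enrolled days on Medicare in each window, and enter it as a time-varying covariate. The share handles patients who change partway through a window.
2. Repeat the out-of-pocket analysis, including the paired comparison, in patients with the same coverage type in both windows. This also reaches the paired t-test, which has no covariates.
3. Tabulate index month by cohort. If it is uneven, add a sensitivity analysis that accounts for index month. A count of January-March days per window would not serve as the adjustment: for July-September index dates it is equal in both windows, yet the deductible model still gives null ratios of 0.81-1.00.

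Cost: enrollment records and dates are already needed for patient selection. The main model loses no patients; the same-coverage repeat omits only those who changed.

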Observed average daily dose (ADD) in claims	Truven: Outpatient pharmacy claims table VHA: Pharmacy file	
The observed insulin ADD will be calculated both in the pre-and post-index periods among the U-500R syringe initiators, U-500 Kwikpen initiators, and the U-500R device switchers. ADD will be reported both as continuous and categorical variable.
 
Pre-index ADD: total number of insulin units/ the total number of days in the pre-index period.
 
Post-index ADD: total number of insulin units/ the total number of days in the post-index period.
 
Additionally the ADD of U-500R syringe only and the U-500R Kwikpen only will be reported in the U-500R syringe initiators and Kwikpen initiators respectively.
 
Note: Total insulin units calculation in based on the similar approach as described in TDD.

Adherence	Truven: Outpatient pharmacy claims table VHA: Pharmacy file	
Adherence to insulin will be assessed using the proportion of days covered (PDC), and reported in categories of 0-20%, 20-40%, 40-60%, 60-80%, and 80%-100%. PDC will be calculated both in the pre-and post-index periods among the U-500R syringe initiators, U-500 Kwikpen initiators ,and the U-500R device switchers.
 
For U-500R syringe initiators (index event 1a):

[2018-7241 Study Identifier] Observational Study Protocol

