		
PDC before U-500R initiation will be calculated as the number of days covered by the prescription claims of insulin (any insulin)/total days in the pre-index period;
 
PDC after U-500R initiation will be calculated as the number of days covered by the prescription claims of insulin (any insulin)/total days in the post-index period.
 
For U-500R Kwikpen initiators (index event 1b):
 
PDC before U-500R initiation will be calculated as the number of days covered by the prescription claims of insulin (any insulin)/total days in the pre-index period;
 
PDC after U-500R initiation will be calculated as the number of days covered by the prescription claims of insulin (any insulin)/total days in the post-index period.
 
For U-500R device switchers (index event 2):
 
PDC before switching will be defined as the number of days covered by the prescription claims of insulin (U-500R syringe)/total days in the pre-index period;
 
PDC after switching will be defined as the number of days covered by the prescription claims of insulin (U-500R Kwikpen)/total days in the post index period
 
Note: For the calculation of PDC in patients with evidence of a basal-bolus regimen, basal/bolus-premixed, or basal/bolus-U-500R, the overlap days will be adjusted for the concomitant use of basal and bolus insulins, but will not be adjusted within basal and within bolus insulins.

--	--	---

[2018-7241 Study Identifier] Observational Study Protocol

Persistence/time to discontinuation	Truven: Outpatient pharmacy claims table VHA: Pharmacy file	Persistence will be defined as the percentage of patients continuing on the index medication in the post-index period. Patient is considered to discontinue if there is no refill of the index medication within 60 days from the run-out date (date of last prescription + days of supply) i.e, a gap of >60 days from the run out date. The run-out date will be the discontinuation date. Time to discontinuation will be defined as the total number of days from the index date to the discontinuation date during the post-index period.
Abandonment/fill rates	Truven: Outpatient pharmacy claims table VHA: Pharmacy file	The average number of insulin prescription fills will be calculated in the pre- and post-index periods among all the study cohorts.

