All-cause health care total and out-of-pocket costs	Truven: Inpatient service table, outpatient service table, outpatient pharmacy claims table	All-cause health care costs for total and out-of-pocket costs including inpatient costs, outpatient costs, pharmacy costs, total costs (inpatient + outpatient + pharmacy), out-of-pocket inpatient costs, out-of-pocket outpatient costs, out-of-pocket pharmacy costs and total out-of-pocket costs (inpatient + outpatient + pharmacy) will be computed among T2DM patients before and after U-500R syringe initiation and U-500R Kwikpen initiation. Costs will be adjusted to 2018 US dollars using the annual medical care and drug costs components of the Consumer Price Index (CPI) to reflect inflation.
---	---	--

Note: When comparing the TDD, ADD, adherence, fill rates and claim gaps in the pre vs post-index periods among the U-500R device switchers, only the claims corresponding to U-500R (syringe in the pre-index and Kwikpen in the post-index) will be considered. To be more specific we will be looking only at the treatment patterns of U-500R alone rather than the regimen.

However, for the U-500R initiators, the regimen use (use of different types of insulin) in the pre-index period will be compared to the regimen use (U-500R + other insulins) in the post-index period.

[2018-7241 Study Identifier] Observational Study Protocol**6. Sample Size and Statistical Methods****6.1 Determination of Sample Size**

The preliminary sample sizes for the VHA databases from 2013-2018 are shown below. This study will use the most recently available 5 years of data.

Table 4. Preliminary Sample Size

Database	Counts
VHA (01APRIL2013-31MARCH2018)	
T2DM (ICD-9: 250.x0, 250.x2) + Humulin R U-500 Kwikpen (NDC: 00002882427, 00002882459)	4,120
≥2 HbA1c measurements	4,066
T2DM + Humulin R U-500 Vial (NDC: 00002850101)	5,863
≥2 HbA1c measurements	5,718

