Numbers and percentages will be provided for dichotomous and polychotomous variables. Means and standard deviations (SDs) will be provided for continuous variables. McNemar's test will be used to determine statistical significance of before and after values for categorical variables, and the paired t-test will be used to assess the statistical significance of before and after values in continuous variables.

Multivariate Analysis

No multivariate analysis will be applied for Secondary Objective 2b.

Research Objective 3: Primary Objective 3Descriptive Analysis

Health care total costs and out-of-pocket costs will be analyzed descriptively before and after U-500R syringe initiation and U-500R Kwikpen initiation. More specifically, among the U-500R initiators, all the variables will be compared before and after U-500R syringe initiators and U-500R Kwikpen initiators.

Numbers and percentages will be provided for dichotomous and polychotomous variables. Means and standard deviations (SDs), along with the median, minimum and maximum will be provided for continuous variables. McNemar's test will be used to determine statistical significance of before and after values for categorical variables, and the paired t-test will be used to assess the statistical significance of before and after values in continuous variables.

Multivariate Analysis

Generalized linear mixed model with log link will be used to evaluate factors associated with total health care costs and out-of-pocket costs in the pre- and post-index periods among U-500R syringe initiators and U-500R Kwikpen initiators. Generalized linear mixed model is used for studies with

[2018-7241 Study Identifier] Observational Study Protocol

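### In the cost mediation, adherence and cost share the same insulin fills, so the indirect effect includes the insulin bill and cannot by itself show an effect of adherence on medical spending

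*Protocol*

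**What the plan says.** Primary Objective 3 concerns syringe and Kwikpen initiators in the Truven claims database. The protocol's Table 3 (section 5.5) defines the variables:

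- Adherence: "Adherence to insulin will be assessed using the proportion of days covered (PDC"). For initiators after the index date it is "the number of days covered by the prescription claims of insulin (any insulin)/total days in the post-index period"; the pre-index version has the same form. The Truven source is the outpatient pharmacy claims table.
- Costs: the components include "pharmacy costs, total costs (inpatient + outpatient + pharmacy") and "total out-of-pocket costs (inpatient + outpatient + pharmacy"). The source is "Truven: Inpatient service table, outpatient service table, outpatient pharmacy claims table".

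In section 6.4.1, the Objective 3 model is to "evaluate factors associated with total health care costs and out-of-pocket costs in the pre- and post-index periods". The mediation that follows says "Adherence is considered as a potential mediator between the costs and time". It regresses adherence on time, then costs on time and adherence. A time effect that vanishes after adjustment is read as full mediation by adherence, and one that shrinks as partial mediation. Indirect, direct and total effects are reported with bootstrap p-values and a percentage mediated.

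The mediation steps neither separate insulin cost from the outcome nor mention the overlap. Mediator, outcome and reading rule are all fixed in the protocol itself.

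**The concern.** The four-step scheme is also used for HbA1c, where the outcome does not contain the mediator. For costs it does, because the fills that make up PDC are paid for in the outcome. The indirect effect therefore adds two quantities: what the extra insulin costs, and any change in other care that goes with better adherence. These may have opposite signs. More fills raise pharmacy spending, while better adherence might lower inpatient and outpatient spending.

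Two misreadings follow. A sizeable percentage mediated could be taken as evidence that adherence changes medical spending when it reflects only the insulin bill. Or a real medical saving could be offset by insulin spending, so that the time effect does not shrink and the reading rule reports no mediation.

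The protocol itself expects PDC to differ between periods: it leaves adherence out of the main cost model on the ground that adherence and time are strongly collinear. Step 2 of the mediation also moves on when time and adherence are significantly related. The overlap thus matters in the very situation in which the mediation result will be reported.

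**Working it through.** The protocol gives no PDC value, insulin price, cost level or expected percentage mediated, so it has no figure to reproduce. The check is algebra from its definitions, followed by an illustration under assumed inputs.

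**Inputs from the protocol.** PDC and cost as defined in Table 3. Observed TDD is insulin units divided by unique days of supply, so units = TDD × days supplied. The period is nine months: 365 × 9/12 = 273.75, taken as 274 days.

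**Algebra.**

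- Insulin cost ≈ price per unit × TDD × PDC × 274.
- Total cost = non-insulin cost + insulin cost.
- Let c be insulin cost per covered day, m the change in non-insulin cost per unit of PDC, and Δ the change in PDC. On a linear scale the indirect effect is Δ × (274c + m).
- The term 274c is the insulin bill, and m is the part that concerns other care. If Δ = 0 the indirect effect is nil. If m = −274c the two parts cancel.
- Adjusting for TDD does not remove 274c: at fixed TDD and price, insulin cost still rises with days supplied.

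**Dollar illustration (c is assumed).** With Δ = 0.10, covered days rise by 0.10 × 274 = 27.4. At c = 20 this is 27.4 × 20 = 548 dollars; at c = 60 it is 27.4 × 60 = 1,644 dollars. A saving of the same amount in other care would be fully offset.

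**Simulation (all inputs assumed).** 100,000 patients, two periods each; mean TDD 220 then 250 units/day; 0.15 dollars per unit; non-insulin cost of 6,000, 12,000 or 20,000 dollars, rising by 500. Non-insulin cost was drawn independently of PDC, so m = 0. Linear and gamma log-link models were fitted without the random effect that the protocol's model has. Ranges cover both models and the three cost levels.

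| PDC before → after | Insulin share of total cost | % mediated, total cost | % mediated, non-insulin cost |
|---|---|---|---|
| 0.60 → 0.60 | 23–49% | −0.7 to 0.1 | 0.0 |
| 0.60 → 0.65 | 24–50% | 25.2 to 28.2 | −1.8 to 0.9 |
| 0.60 → 0.70 | 25–51% | 37.4 to 44.4 | 0.6 to 3.0, one run −11.5 |
| 0.70 → 0.60 | 24–51% | −247.5 to −500.6 | −1.6 to −5.9 |

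The −11.5 is sampling noise at the highest non-insulin cost level.

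**Cross-check against the algebra.** Average TDD is (220 + 250)/2 = 235. The simulated doses have a log-scale SD of 0.3, which multiplies the mean by exp(0.3²/2) = 1.046, giving 245.8 units. Then c = 245.8 × 0.15 = 36.87 dollars, and 274c = 10,102 dollars per unit of PDC. Truncation of PDC made the realised rises 0.048 and 0.095. The expected indirect effects are 10,102 × 0.048 = 485 and 10,102 × 0.095 = 960 dollars. The linear runs gave 476–493 and 898–978.

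**The case against.** The strongest reply is that insulin spending is a real pathway. Primary Objective 3 asks how adherence relates to total and out-of-pocket costs. If patients fill more insulin, both payer and patient do spend more, and an indirect effect on total cost measures that net result. This stands. A reader might infer that the percentage mediated is a mere arithmetic artefact without meaning, or that total cost should be confined to description. The documents support neither: the first ignores a real expense, and the second would drop the mediation on the objective's own outcomes.

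It also stands that the link is not an identity. PDC counts days, with an adjustment for concurrent basal and bolus insulin, while cost follows quantity and price. Fewer fills with a longer supply can raise PDC, and cost per covered day can change with the regimen.

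A third reply is that inpatient, outpatient and pharmacy costs are each computed before and after initiation, so a fall in medical cost would be visible. That is right, but such a fall would not be tied to adherence, which is the mediation's purpose.

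Finally, the large negative percentages when PDC falls come from direct and indirect effects of opposite sign. Any percentage-mediated statistic has that weakness, so they should not be counted as evidence specific to shared claims.

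**Conclusion.** The point holds as a limit on interpretation, not as a contradiction or a calculation error. By the protocol's definitions the mediator and both cost outcomes draw on the same insulin fills. Whenever PDC changes, the indirect effect and percentage mediated include insulin spending, and an offsetting effect on medical cost could be masked.

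The actual size is unknown. It depends on the PDC change, the insulin share of cost and the total effect of time, none of which the protocol gives, and it is nil without a change in PDC. The dollar range and the roughly 25–44% mediated for rising PDC rest wholly on assumed inputs. They show that the overlap can matter, not how large it will be in these data.

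**What to change.** - Keep the planned mediation on total and out-of-pocket cost, and state that its indirect effect includes spending on the insulin fills that define PDC.
- Add the same mediation for medical cost (inpatient + outpatient) and for out-of-pocket medical cost. Table 3 already has these components computed.
- Base any statement about adherence and medical spending on the medical-cost mediation.
- Optionally, add total cost without insulin claims. This is not among the listed components, so the insulin claims must be separated with the NDC codes the study already holds.

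The cost is a little programming and some further tests: two added outcomes in two initiator cohorts make 2 × 2 = 4 more mediation analyses, plus two if the optional outcome is used. Section 6.3 applies no multiplicity adjustment, so these should be presented as supporting the interpretation of the planned result.
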